## **SPECIFIC AIM 2: Define the IL-5-elicited molecular features of upper airway nasal epithelial tissue from subjects with healthy sinus mucosa, CRSwNP, and AERD.**

**Overview.** Bronchial epithelial cells and human sinonasal tissue epithelial cells express a functional IL-5R $\alpha$ . Further, *in vivo* inhibition of IL-5 leads to transcriptional modification of upper respiratory tract epithelial cells. In this aim, we will test the ***hypothesis that IL-5 actions on the human upper airway epithelium to reduce cell-to-cell adhesions by downregulating tight junction pathways and impacting transcripts related to cell-to-cell adhesion.***

**Methods.** We have already established a protocol that for the first time, shows the development of IL-5R $\alpha$  on upper airway (nasal) epithelial cells. Sinonasal epithelial cells expanded to an air liquid interface culture begin to express detectable levels of IL5RA by week 2 and appear to reach maximal IL5RA transcript expression after 4 weeks in culture, which parallels their development of cilia and their expression of FOXJ1, a transcript that directly regulates genes involved in ciliary structure assembly and motility (**Figure 5**). Using this culture system, we will now explore the function of IL-5 signaling on these cells. Sinonasal epithelial cells will be harvested from 10 donors with CRSwNP, 10 donors with AERD, and 10 healthy donors undergoing correction of upper airway anatomic abnormalities. Epithelial cells will be expanded to passage 3 (week 4-5) in an air liquid interface culture and will be stimulated with IL-5 at 3 increasing doses for 24–48 hours. Additionally, to assess any possible chronic effects of IL-5, a portion of the air liquid interface cultures will be grown in low-dose IL-5 added into their media from week 1 (in order to more closely approximate the environment of respiratory inflammation with the constant presence of IL-5 that exists in the sinuses of patients with CRSwNP). These sets of cultured and chronically and/or acutely stimulated or unstimulated epithelial cells will then be stored for RNA and protein measurements. They will be assessed by qPCR for expression of *IL5RA*, *CDH1* (E-cadherin), *CAV1* (caveolin-1), *CAV2* (caveolin-2), *EGFR* (epidermal growth factor receptor), *CXCLA*,

*CXCL1*, *IL10RA*, *IL1RL1* (ST2), and *IL6R*, as these transcripts are known to be impacted by IL-5 stimulation in the lower airway. We will also measure IL-5R $\alpha$  protein levels by Western-blot in these epithelial cells. To more broadly assess the effects of IL-5 signaling on human nasal polyp epithelial cells and to assess for yet-unidentified impacts of IL-5/IL-5R $\alpha$  signaling on these cells, we will collect IL-5 stimulated/unstimulated sinus tissue epithelial cell pairs for bulk RNA-sequencing with Smart-seq2.

**Anticipated results.** We suspect that the sinus tissue epithelial cells from diseased patients (CRSwNP and AERD) will express higher levels IL-5R $\alpha$  compared to healthy control tissue, and/or that their development of IL5RA expression will happen earlier in the maturation process compared to healthy control epithelial cells. We suspect that IL-5 stimulation of sinus tissue epithelial cells will identify downregulation of transcripts related to cellular adhesion and tight junction pathways and enrichment of a T2 immune signature.

**Statistical Analyses.** Differential expression analysis of RNA-seq data will be conducted using the DESeq2 package for R taking patient origin into account. Following normalization, DESeq2 will be run in a pairwise manner by comparing stimulated/unstimulated cell pairs, identifying significantly differentially expressed genes (DEGs). For pathway analyses, WebGestalt online tool will be used to identify the distribution of pre-ranked DEGs involved in specific signaling pathways in Gene Ontology Biological Processes database.

**Pitfalls and Alternative Approaches.** The molecular analysis of human upper airway epithelial cells is based on prior study of the human bronchial epithelial cells. However, if the pre-selected qPCR markers do not detect measurable differences between IL-5 stimulated and unstimulated cells, RNA-sequencing allows for unbiased analyses and may detect yet-undescribed changes mediated by IL-5. Further, if the molecular analyses do not identify IL-5-elicited changes in sinus tissue airway epithelium, we can plan functional phosphorylation studies on the sinus tissue airway epithelial cells as described in **Aim 1b**.

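### Aim 2 states a tight-junction and adhesion hypothesis but names no gene set, primary contrast or decision rule by which to judge it

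*Combined protocol and SAP*

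**What the plan says.** All references are to the Combined protocol and SAP.

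- **Hypothesis (Specific Aim 2, Overview).** The aim is to test whether IL-5 reduces adhesion between upper-airway epithelial cells by "downregulating tight junction pathways and impacting transcripts related to cell-to-cell adhesion".
- **Targeted measurement (Aim 2, Methods).** Ten transcripts are measured by qPCR: IL5RA, CDH1, CAV1, CAV2, EGFR, CXCLA, CXCL1, IL10RA, IL1RL1 and IL6R. They were chosen "as these transcripts are known to be impacted by IL-5 stimulation in the lower airway". The only protein measurement named is a Western blot for the IL-5 receptor.
- **RNA sequencing (Aim 2, Methods).** Its role is broad: "to assess for yet-unidentified impacts of IL-5/IL-5R $\alpha$ signaling on these cells".
- **Expectation (Aim 2, Anticipated results).** IL-5 stimulation "will identify downregulation of transcripts related to cellular adhesion and tight junction pathways and enrichment of a T2 immune signature".
- **Analysis (Aim 2, Statistical Analyses).** "DESeq2 will be run in a pairwise manner by comparing stimulated/unstimulated cell pairs". Then the "WebGestalt online tool will be used to identify the distribution of pre-ranked DEGs involved in specific signaling pathways in Gene Ontology Biological Processes database". No gene set, threshold or rule for success is given. The section does not cover the qPCR data.
- **Conditions (Aim 2, Methods).** There are ten donors in each of three groups, three IL-5 doses over 24 to 48 hours, and a chronic low-dose condition. None of these is named as the primary contrast.

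**The concern.** The hypothesis is specific: it names a mechanism and a direction. The analysis is general: it ranks whatever changed and looks across a database. Nothing in the plan says which result would count for the hypothesis and which against it.

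That gap can mislead in two ways. If the GO results are corrected across all the sets examined, a true fall in tight-junction transcripts competes with every other pathway and may not pass. If they are not corrected, or if terms are selected by eye, some adhesion-like term among many may look supportive by chance and be reported as confirmation. In either case the aim could finish without a clear answer to the question it poses.

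**Working it through.** The plan gives no power, alpha or effect size for Aim 2, so there is no figure of its own to reproduce. The check has two parts.

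**1. Hypothesis against measurement and analysis**

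| Part of the hypothesis | qPCR panel | RNA-seq, gene level | RNA-seq, pathway level |
|---|---|---|---|
| Adhesion transcripts | 1 of 10 (CDH1, E-cadherin) | Measured; no threshold stated | No set named |
| Tight-junction pathway | 0 of 10 (no claudin, occludin or ZO transcript) | Measured; no threshold stated | No set named |

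By contrast, Sub-Aim 1b (Methods, part B) does state a gene-level criterion: more than twofold change with a false discovery rate below 1%. Aim 2 has no counterpart at gene or pathway level.

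**2. What an open scan could cost (illustration)**

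Assumptions, none of them in the documents:

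- The tight-junction set has a test statistic centred at z = 3.
- Testing is at 5%, two-sided.
- Bonferroni correction is applied over m sets, with m = 1, 100, 1,000 or 5,000.

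Formula: power = 1 − Φ(z_crit − 3), where z_crit is the upper 0.05/(2m) point of the standard normal distribution.

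| m | z_crit | z_crit − 3 | Power |
|---|---|---|---|
| 1 | 1.960 | −1.040 | 85.1% |
| 100 | 3.481 | 0.481 | 31.5% |
| 1,000 | 4.056 | 1.056 | 14.6% |
| 5,000 | 4.417 | 1.417 | 7.8% |

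Bonferroni is close to the worst case. I also simulated Benjamini–Hochberg control at 5% with independent sets, a further assumption:

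- If 10% of sets carry a z = 3 effect, power for any one of them is about 50% at 100, 1,000 or 5,000 sets.
- If 5% do, it is about 40%.
- If the target set is the only active one, it falls back to roughly the Bonferroni values.

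**With two pre-named directional sets.** Holm's strictest step is 0.05/2 = 0.025 one-sided, so z_crit = 1.960 and power is again 85.1% at z = 3. Naming two sets rather than one, with direction down, therefore costs nothing against the two-sided single-set figure.

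**The case against.** A reader might infer from the mismatch that the hypothesis is not tested at all. The documents do not support that. CDH1 is an adhesion transcript and is measured in stimulated and unstimulated cultures. Paired DESeq2 compares every detected adhesion and tight-junction gene between conditions. Anticipated results commits in writing to both families and to the direction, which narrows the room for choosing terms afterwards. It does not close it, because each family could be represented by more than one GO term and no threshold is set.

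Three further points on the other side have weight:

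- **An open scan is an inference.** The pathway sentence speaks of specific pathways without listing them. That could mean a chosen few, but if so they are not identified.
- **The panel is reasonable for its purpose.** The aim's title is about defining IL-5-elicited features, and transcripts with a known lower-airway response fit that. The absence of tight-junction primers is not in itself a fault.
- **This is observational laboratory work.** No treatment decision hangs on Aim 2. Even so, the Overview uses the language of hypothesis testing, and an aim meant as exploratory should say so.

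The blinding section does not answer the concern. It conceals disease state, whereas the choice at issue is among GO terms in a stimulated-versus-unstimulated comparison.

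**Conclusion.** The concern holds in a limited form. Aim 2 bears on its hypothesis through one adhesion transcript, gene-level paired testing and an open pathway analysis. It lacks a pre-named gene set, a primary contrast and a decision rule.

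The power figures (85% for one named set, against about 32%, 15% and 8%) show how the loss arises. They should not be read as the expected loss. They depend on the assumed z of 3, the assumed numbers of sets and a Bonferroni rule that the plan never states. Under false discovery rate control with other active sets the loss is smaller, at roughly 40% to 50% power in the cases simulated. GO sets also overlap, which neither calculation reflects.

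This is a modest weakness with a cheap remedy. It is not a flaw that invalidates the aim.

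**What to change.** Before the Aim 2 data are analysed, add to Aim 2, Statistical Analyses, text to this effect:

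> The primary pathway analysis of Aim 2 tests two gene sets fixed in advance by database identifier and version: one tight-junction set and one cell-cell adhesion set. All tested genes are ranked by the paired DESeq2 statistic for one primary stimulated-versus-unstimulated contrast, named in advance from the conditions already planned. Each set is tested for downregulation, with Holm adjustment across the two tests at 5%. The analysis of the full GO Biological Processes database, and all other contrasts, are exploratory.

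The investigators should choose the contrast (dose, duration and donors included). What matters is that it is fixed beforehand. Ranking all genes, rather than only those declared differentially expressed, avoids dependence on a gene-level cut-off that Aim 2 does not state.

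The cost is a short addition to the plan and a commitment made in advance. A set that moves upward would not count as support, although it would still be seen in the exploratory scan. No extra samples or assays are needed. The selection section says Aim 2 samples are all to be collected prospectively, so the choice can be recorded before results are seen. Adding tight-junction primers to the qPCR panel is optional and not required for this fix.

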#### **Sub-Aim 1a. Use RNA sequencing to characterize the transcriptional profile of nasal polyp plasma cells in nasal polyps from patients with AERD and aspirin-tolerant CRSwNP.**

**Methods.** Sinus tissue from 6 subjects with AERD and 6 subjects with aspirin-tolerant CRSwNP has been obtained. Subjects were be matched for age, gender, and intranasal corticosteroid use. Freshly excised tissue was digested into a single cell suspension. Using a

BD FACSaria Fusion Cell Sorter, plasma cells were purified and collected in TCL buffer for storage. Going forward, 1000 cells from each patient phenotype will be used for low-input RNA sequencing, and the remainder set aside for qRT-PCR analysis. RNA will be sequenced with Smart-seq2 using the Broad Institute Technology Labs facilities. Unbiased differential gene expression will be characterized using the Kallisto program to map reads to the genome, taking into account uncertainty in read mapping. To identify gene sets that may relate to biologically relevant differences in cellular function we will utilize linear mixed models. To confirm expression results from our RNA sequencing, we will validate the gene quantification of the top 5 differentially expressed genes within the plasma cell populations with qRT-PCR, using commercially available primers.

**Anticipated Results.** We expect that the transcriptional signature of the plasma cells from patients with AERD will show increased cell survival and activation. We expect that these cells will show upregulation of transcripts involved in activation of the cell cycle (*CCND2*), antiapoptotic genes (*BCL2*, *CFLA/R*), and those encoding surface receptors and adhesion molecules (*IL5RA*, *ICAM1*, *CD9*), along with downregulation of negative regulators of the cell cycle (*KLF2*, *KLF6*). We predict that the plasma cells in nasal polyps from patients with AERD will have higher *IL5RA* expression overall, and will express more *IGHG4* and *IGHE* transcripts, suggesting that the overproduction of nasal IgE in inflamed tissues may be driven in part by IL-5 signaling.

**Sub-Aim1b. Determine the functional significance of IL-5R $\alpha$  expression and IL-5 signaling on the plasma cells in nasal polyp tissue.**

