and banked for low-input RNA sequencing as above. Going forward, we will conduct differential expression analysis on IL-5-stimulated and unstimulated plasma cells using sample pairing, with a linear model framework. Our criterion for transcripts induced or repressed by IL-5 is that genes are more than twofold changed and obtain a false discovery rate of <1%.

**Anticipated Results.** **(A)** Plasma cell populations with higher IL-5R $\alpha$  expression should exhibit increased phosphorylation of JAK1, JAK2, STAT1, and STAT5 and should demonstrate further increases upon stimulation with IL-5. **(B)** We expect to confirm that IL-5 stimulation of nasal polyp plasma cells induces expression of *CCND2*, *JAK1*, *IKZF1*, *ZBTB44*, *OTG*, *RAP1B*, and *RAC2*, as well as signatures reflecting activation and anti-apoptotic signals (*BCL6*, *AID*, *BLIMP-1*).

**Statistical Analyses.** With a sample size of 6 AERD subjects and 6 CRSwNP subjects, we will be powered at >90%, at a 0.05 level of significance, to detect a difference in antibody-secreting cells that express IL-5R $\alpha$ + between subjects with AERD and CRSwNP. The data will be analyzed as described in Aim 2.

**Pitfalls and Alternative Approaches.** Although the proposed work is largely hypothesis based and furthers recent preliminary observations made by our group, low-input RNA sequencing allows for unbiased analyses. Thus, while we focus on the role of IL-5R $\alpha$ + plasma cells in CRSwNP and AERD pathogenesis, our approach also allows us to identify a range of differentially expressed genes and to broadly phenotype nasal polyp plasma cells.

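### Minor, cheap improvement: as worded, the Aim 2 pathway step ranks only significant genes, which costs sensitivity to modest tight-junction or adhesion downregulation; rank all tested genes and use a correlation-aware set test

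*Combined protocol and SAP*

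**What the plan says.** Specific Aim 2, Statistical Analyses, describes two steps. In the gene-level step, "DESeq2 will be run in a pairwise manner by comparing stimulated/unstimulated cell pairs, identifying significantly differentially expressed genes (DEGs"). In the pathway step, the "WebGestalt online tool will be used to identify the distribution of pre-ranked DEGs involved in specific signaling pathways", with Gene Ontology Biological Processes as the database.

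The section does not state the enrichment method (rank-based or over-representation), the ranking statistic, the reference set, the cut-off that makes an Aim 2 gene a DEG, or the error control across pathways. The only DEG cut-off in the document (more than twofold change with FDR below 1%) is in Sub-Aim 1b.

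The hypothesis in the Aim 2 Overview is that IL-5 acts on the epithelium "to reduce cell-to-cell adhesions by downregulating tight junction pathways and impacting transcripts related to cell-to-cell adhesion". The Aim 2 Anticipated results expect "downregulation of transcripts related to cellular adhesion and tight junction pathways and enrichment of a T2 immune signature". No effect size is given. WebGestalt is the only pathway-level analysis named for Aim 2. Sub-Aim 1a has its own gene-set method: "To identify gene sets that may relate to biologically relevant differences in cellular function we will utilize linear mixed models".

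**The concern.** The word DEG is defined by significance in one sentence and used as the input to a ranked analysis in the next. Taken at face value, the ranked list contains only genes that passed the filter.

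That matters for a pathway hypothesis. A rank-based set test gains power by accumulating many small shifts in one direction, measured against all the genes that did not move. Filtering first removes most of the small shifts and also the unmoved genes that serve as the comparison. What is left compares a few pathway genes with other significant genes.

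At stake is a missed tight-junction or adhesion signal in the one pathway analysis that addresses the Aim 2 hypothesis. The Aim 2 Pitfalls paragraph relies on RNA sequencing if the chosen qPCR markers show nothing, and a modest, spread-out effect is most relevant in that situation. In addition, if the input list and method are left open, they can be chosen after the results are seen.

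**Working it through.** **No plan figure to reproduce.** The documents give no power, effect-size or error-rate figure for the pathway step. The only power statement (above 90% with 6 against 6, Aim 1) concerns IL-5Rα-positive cells and does not bear on this point.

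**Assumed inputs, none from the documents.** 12,000 genes; a 60-gene pathway, every gene with the same mean shift; 5% of other genes changed at |mean z| of 3 or 4, half up and half down; within-set correlation ρ of 0.05, 0.10 or 0.20; DEG cut at Benjamini-Hochberg 5%.

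**Step 1: how many pathway genes reach the DEG list?** The cut-off c solves 12,000 × 2[1 − Φ(c)] / (expected DEGs) = 0.05. It is about 3.29 when the changed genes sit at |z| = 3 and about 3.07 when they sit at 4. The expected number of pathway DEGs for a shift δ is 60 × Φ(δ − c). The pathway's own DEGs lower c slightly (to 3.25 and 3.05 at δ = 3).

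- δ = 1: 0.7 to 1.2
- δ = 1.5: 2.2 to 3.5
- δ = 2: 6.0 to 8.6
- δ = 3: 24 to 29

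So at a shift of 1 z about one gene in 60 enters the list.

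**Step 2: what does the full list see?** The mean of the 60 correlated z-scores has SD = √[(1 + 59ρ)/60] = 0.257, 0.339, 0.462 for the three ρ. A calibrated one-sided 5% test has approximate power Φ(δ/SD − 1.645). At δ = 1 this is 0.99, 0.90, 0.70.

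**Step 3: simulated detection, one-sided p<0.05, single set.** Ranking rows cover a Mann-Whitney and a weighted Kolmogorov-Smirnov test. Sets with fewer than 5 DEGs count as not detected.

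| Method | −1 z | −1.5 z | −2 z | −3 z |
|---|---|---|---|---|
| All genes ranked, calibrated for correlation | 69-99% | 94-100% | 100% | 100% |
| DEGs only, ranked | 0-4% | 0-20% | 16-59% | 84-100% |
| Over-representation, up and down pooled | 0-4% | 15-24% | 60-75% | 99-100% |

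The pooled over-representation row is unfair to that method, because the ranking tests were directional. Using down-regulated DEGs only, and without the 5-gene minimum, over-representation gave about 5-11% / 31-45% / 66-90% at −1 / −1.5 / −2 z. It remains below all-gene ranking, by less.

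**Step 4: a different design.** Assume 15,000 genes, a 100-gene set with half its genes shifted, 300 other genes at log2 fold change ±1.5, independent genes, and SD of the paired difference 0.5 or 0.8. With 10 pairs (the plan's donors per group) and a shift of −0.2 on the log2 scale, 0.4 to 1.2 set genes became DEGs at FDR 5%. All-gene ranking detected the set in 97-100% of replicates and DEG-only ranking in 0%. With these stronger background genes, DEG-only ranking still detected nothing at −0.6 (SD 0.5, FDR 5%), although about 36 set genes were DEGs and over-representation detected the set every time. How fast the loss closes therefore depends on the other changed genes.

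**Step 5: false positives of a simple all-gene test.** If a one-sided 5% test ignores correlation, its approximate null rejection rate is 1 − Φ(1.645/√(1 + 59ρ)) = 0.20, 0.27, 0.32. Simulation under the first set of inputs gave 19-34%. In the Step 4 design the rate rose to 16%, 40% and 54% at ρ = 0.01, 0.05 and 0.10. All-gene ranking therefore needs a correlation-aware test to go with it.

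**The case against.** **The harm depends on one reading.** The word pre-ranked may be loose shorthand for the full DESeq2 ranking, in which case nothing is lost. It may be a misnomer for over-representation, for which a DEG list is a proper input. The sentence could even describe plain sorting into categories with no test. This stands: the documents establish an unclear input and method. A reader might infer that a faulty test is definitely planned; the text does not go that far.

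**The percentages do not describe the remedy.** They are for one set at one-sided p<0.05 with known correlation, whereas the remedy controls FDR across many sets. With the Step 2 formula, power at −1 z falls from 0.99, 0.90, 0.70 to 0.79, 0.44, 0.18 at an assumed p<0.001. The other methods would fall too, so the ordering is expected to hold, but the figures do not carry over. This stands.

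**All-gene ranking alone could replace lost sensitivity with false positives.** This stands as well, and is why the correlation-aware test is a required part of the fix. The opposite inference, that the DEG filter itself inflates false positives, has no support: DEG-only Mann-Whitney ranking rejected 0% under no effect.

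**The stakes are low.** The RNA sequencing is exploratory, the qPCR panel includes CDH1, gene-level results are unaffected, and the pathway step can be repeated from the full DESeq2 output. This limits the severity. A few single genes still do not test a pathway.

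**Conclusion.** The point holds as a minor one: a cheap improvement to an exploratory analysis. On the literal wording, Aim 2 ranks a significance-filtered list and loses sensitivity to modest coordinated shifts in the pathways it hypothesises about. On the full-list reading there is no loss. On the over-representation reading the input is valid, with a smaller loss of sensitivity to modest shifts.

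The size rests entirely on assumed inputs. In the main illustration the loss is large at −1 to −2 z and nearly gone at −3 z. The direction is the same in both designs; the percentages are illustrative only.

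A reader might infer that the Aim 2 findings would be invalid, or that the same flaw runs through Aim 1 because its statistical paragraph refers to Aim 2 for the data analysis. Neither follows. The DESeq2 gene-level analysis is untouched, and Sub-Aim 1a names its own gene-set method.

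**What to change.** Replace the pathway sentence under Specific Aim 2, Statistical Analyses, with:

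> All genes passing the expression filter will be ranked by the signed DESeq2 statistic from the paired model and entered into pre-ranked enrichment analysis in WebGestalt (GO Biological Process), with FDR control across sets. The tight-junction and adhesion sets will be named in advance, and the conclusion on them will rest on a set test that allows for inter-gene correlation, run on the same data.

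The second sentence is required and should not be dropped as optional.

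If over-representation is what the sponsor intends, name it, state the Aim 2 DEG cut-off, test up- and down-regulated genes separately, use all expressed genes as the reference set, and note that modest shifts may be missed.

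Cost: two sentences, the same data, no new samples or assays. The downside is a little more analysis work and a stricter test for the named sets.

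### Aim 2 pathway tests start from a pre-ranked gene list, so the set-level null omits donor-level co-variation; the error is inflated mainly if all genes are ranked

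*Combined protocol and SAP*

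**What the plan says.** The Aim 2 hypothesis (Specific Aim 2, Overview) is itself a pathway claim: IL-5 is expected to "reduce cell-to-cell adhesions by downregulating tight junction pathways". The cells come from "10 donors with CRSwNP, 10 donors with AERD, and 10 healthy donors undergoing correction of upper airway anatomic abnormalities".

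The Statistical Analyses paragraph of Aim 2 has three steps:

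- Gene level: "Differential expression analysis of RNA-seq data will be conducted using the DESeq2 package for R taking patient origin into account".
- Contrast: "DESeq2 will be run in a pairwise manner by comparing stimulated/unstimulated cell pairs, identifying significantly differentially expressed genes (DEGs".
- Pathway level: "WebGestalt online tool will be used to identify the distribution of pre-ranked DEGs involved in specific signaling pathways in Gene Ontology Biological Processes database".

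The plan does not say whether the ranked list holds every tested gene or only the significant ones. It also gives no ranking metric, set statistic, null distribution, background list, or pathway p-value or FDR cut-off. The numerical criteria given elsewhere belong to other questions. Sub-Aim 1b, Methods (B), requires that "genes are more than twofold changed and obtain a false discovery rate of <1" per cent, which is a gene-level rule. The Statistical Analyses paragraph closing Aim 1 states "we will be powered at >90%, at a 0.05 level of significance", which concerns a cell-population comparison.

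**The concern.** A ranked list with one number per gene contains no samples. A test built on it cannot rearrange or rotate donors, so its null has to treat genes as exchangeable and, in effect, independent. Genes in one pathway tend to move together within a donor. If one donor's two wells differ by chance through handling or culture maturity, many genes of a set shift together, and the set test counts that shift as many separate confirmations.

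At stake is the claim that IL-5 changes tight-junction and adhesion pathways. The Pitfalls paragraph of Aim 2 also makes RNA sequencing the fallback if the pre-selected qPCR markers show nothing. In that case a pathway result could become the main finding.

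**Working it through.** **Inputs from the documents.** Paired stimulated/unstimulated samples; 10 donors per group, 30 in all; a donor-aware DESeq2 model; a pre-ranked list at the pathway step. There is no plan figure to reproduce, because no error rate or power is stated for the pathway analysis.

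**Assumptions not in the documents.** Nominal two-sided 5%; set size m of 50 or 100; mean within-set correlation rho of the paired differences of 0.02 to 0.10; a gene-label null, inferred from the form of the input.

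**Step 1: full list, no gene responds, by formula.** The mean of m unit-variance gene statistics has variance [1 + (m−1)·rho]/m, where the gene-label null assumes 1/m. The true error is therefore

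2·[1 − Φ(1.96/√(1 + (m−1)·rho))].

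For m = 100 and rho = 0.02: 1 + 99 × 0.02 = 2.98; √2.98 = 1.726; 1.96/1.726 = 1.135; error 25.6%. The number of donors does not appear in the formula.

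**Step 2: the same case by simulation.** Paired donor differences were generated with a shared donor factor inside the set. A paired t was computed per gene, followed by a gene-label rank-sum test. Ranges are over repeated sets of runs.

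| rho | Formula, m = 50 | Formula, m = 100 | Rank-sum, m = 100, 10 pairs | Rank-sum, m = 100, 30 pairs |
|---|---|---|---|---|
| 0 | 5.0% | 5.0% | 4.5% | 5.2% |
| 0.02 | 16.4% | 25.6% | 23–27% | 22% |
| 0.05 | 29.1% | 42.2% | 39–44% | 39–42% |
| 0.10 | 42.0% | 55.3% | 52–55% | 52–56% |

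A running-sum (GSEA-type) test with m = 100 gave 16–48% over rho 0.02–0.10, against 3–7% at rho 0, and 30 pairs were no better than 10. The overall range of roughly 16–55% runs from the lowest running-sum figure to the formula at rho 0.10.

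**Step 3: full list, many genes respond.** Here 10% of genes outside the set were shifted by 1 SD (an assumption), with m = 100, a running-sum test and 200 runs.

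| rho | 10 pairs | 30 pairs |
|---|---|---|
| 0.02 | 2.0% | 1.0% |
| 0.05 | 12.5% | 8.0% |
| 0.10 | 29.0% | 16.5% |

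A separate set of runs with true responders gave about 4–27%. The simulation standard error near the top is √(0.29 × 0.71/200) = 3.2 points, so the upper ends agree. A rank-sum test stayed at about 13–50% with responders present, so the answer depends on a set statistic that the plan does not name.

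**Step 4: only significant genes ranked.**

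- Genes chosen at Benjamini–Hochberg 5%, set with no affected genes: 0 false calls in 300 runs in every scenario, up to rho 0.4.
- Genes chosen at unadjusted p < 0.05, rho 0.1–0.2: 0% to 6.2%.
- 20% of genes responding, genes chosen by FDR: 2.5–10% in one set of runs. In another, with equal response inside and outside the set, 7–12% at rho 0.05–0.10 against 4–6% at rho 0. A plain over-representation count there gave about 4%.

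**Step 5: tests that keep the co-variation.** A correlation-adjusted competitive test held 1.5–6.5%. A within-donor sign-flip held 3.8–6.0%, but it tests a different hypothesis (see the change proposed).

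**The case against.** The strongest reply is that the wording points to significant genes only. The plan defines DEGs as significantly differentially expressed and then ranks DEGs. On that reading the large error rates do not apply, as Step 4 shows. This stands, and it is why the size has to be given separately for each reading. It does not close the point: the word pre-ranked suggests a rank-based test, the text does not exclude a full list, and some inflation remains when many genes respond.

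A reader might infer that the pathway analysis ignores donors altogether. The documents do not support that. The DESeq2 model takes patient origin into account, so donor variation enters every gene's statistic and is missing only from the set-level null.

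A reader might also infer that more donors can never help. That holds when nothing responds. With true responders and a running-sum test, the error fell between 10 and 30 pairs. The documents themselves expect a response: the Aim 2 Overview cites transcriptional change in the upper airway when IL-5 is inhibited.

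Finally, the pathway p-values are not the only evidence. The Methods measure *CDH1*, *CAV1* and *CAV2* by qPCR, and RNA sequencing is presented partly as discovery. This stands and lowers the severity.

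**Conclusion.** The point holds in a limited form. The set-level null has no donor-level variation and treats co-varying genes as independent. For a 100-gene set at nominal 5% and an assumed rho of 0.02–0.10:

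- **All genes ranked, no response to IL-5:** true error roughly 16–55%.
- **All genes ranked, many genes responding:** about 4–27% for a running-sum test, falling with more donors.
- **Only FDR-significant genes ranked:** no inflation if nothing responds, up to about 10% otherwise.

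Correlation, set size and the gene-label null are assumptions. It is tempting to turn these rates into an expected number of false pathways across the whole Gene Ontology screen. The documents do not support such a figure: they give no number or size of sets and no pathway cut-off, and Gene Ontology sets overlap. Severity is low to moderate.

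**What to change.** Base the pathway p-values on a correlation-adjusted competitive test (CAMERA), run on all tested genes with the donor-blocked model and with the inter-gene correlation estimated from the data. Apply FDR to those p-values, state the cut-off in advance, and keep WebGestalt for display. This is the like-for-like replacement, because it still asks whether a set changes more than the other genes.

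For the tight-junction and adhesion sets, named beforehand, a rotation test (ROAST/fry) or a within-donor sign-flip may be added. Label these as self-contained tests: they ask whether any gene in the set changes, so they are not interchangeable with the competitive test. With 10 pairs the smallest two-sided sign-flip p-value is 2/2^10 = 0.002, which is too coarse for a full screen.

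The cost is a few sentences in the plan and a standard R function on the same data. The downside is some loss of power and fewer pathways called significant.
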